5.7.2.4.2 Supportive Care for Subjects with GvHD

Supportive care of subjects with GvHD will be administered according to local regulations and standards of care and institutional and international guidelines. The care could include, but is not limited to, the following:

- Oral decontamination and oral hygiene.
- Antibacterial, antiviral, antifungal prophylaxis; notably for: cytomegalovirus (CMV), gram positive (encapsulated) bacteria, *Pneumocystis carinii* and fungal infections per institutional practice.
- Monitoring and treatment of CMV, Epstein-Barr virus (EBV), human herpesvirus 6 and adenovirus viremia (for "matched unrelated donor" follow specific Epstein-Barr virus monitoring). CMV and EBV are to be recorded in the eCRF at screening and Day 28 and Day 56.
- Transfusions of erythrocyte and platelet concentrates; all blood products must be leukocyte depleted and irradiated.
- Antiemetic prophylaxis and pain therapy.

A publication by the EBMT-ELN proposes guidelines that could be used in transplantation centers ([Ruutu et al., 2014](#)).

5.8 Salvage Treatment

There are currently no recommended salvage (third-line) therapies for steroid-resistant acute GvHD; recommended treatment at this point could follow the EBMT-ELN guidelines ([Ruutu et al., 2014](#)) or ASBMT ([Martin et al., 2012](#)), per investigator discretion.

In case of salvage treatment, subjects randomized to BEGEDINA, may be continued BEGEDINA according to the scheduled dose (up to Day 28), along with third-line therapy. For subjects randomized to conventional treatment, the initial conventional treatment may be administered with a third-line therapy. BEGEDINA is not permitted as salvage (third-line) treatment in the conventional treatment arm.

5.9 Management of a GvHD Flare

An acute GvHD flare is defined as worsening of acute GvHD in any organ by at least one stage beyond Study Day +28, subsequent to achieving PR or CR to Initial Therapy.

Subjects who have been randomized to the BEGEDINA arm and who have a GvHD flare after Study Day 28 and before Study Day 90 may receive additional BEGEDINA treatment as follows:

- Subjects must have had documented CR or PR at Day+28.
- Treatment consists of the Initial Therapy Plan (i.e. 5 consecutive days plus days 10, 14, 17, 21, 24 and 28 from the start of the flare) as in the Schedule of Events (Table 19).
- Subjects are recommended to remain in the hospital for treatment of flare, however, at the discretion of the investigator, may be treated in day-hospital facilities; subjects must be monitored (under hospital observation through 2 hours after the start of the infusion) and as per the Schedule of Events (Table 19), with special attention to risk of infusion related reactions (5.1.1.1, 6.2.1.5).[?]
- If a subject has begun other steroid-resistant acute GvHD therapy within the active study treatment period (up to and including Day 28), they would not be eligible to receive further BEGEDINA therapy.

Subjects in the conventional treatment arm may continue or restart therapy as per investigator judgment.

5.10 Worsening of Acute GvHD

Protocol guidelines for increasing the steroid dose for worsening of acute GvHD disease include:

1. Worsening of symptoms for at least 3 days despite second line treatment.

or
2. Grades III-IV acute GvHD persisting for at least 1 week despite second line treatment.

or
3. Grade II acute GvHD persisting for at least 2 weeks despite second line treatment.

Escalation of steroid therapy prior to Day 28 does not constitute withdrawal of a subject from the study. If escalation of therapy occurs, the subject is to continue on study and receive all treatments and assessments per protocol.

If worsening of GvHD requires a third-line agent, please follow instructions as on [Section 5.8](#) for salvage therapy.

5.11 Dose Modification for Toxicity

No specific toxicities have been observed to date with BEGEDINA.

Important identified risks include the development of HAMA and infusion-related reactions (described in Section 5.1.1).

Therefore, dose modification for toxicity is left to the discretion of the Principal Investigator. However, treatment should be delayed/withdrawn in case of severe (Grade 3 or above) toxicity considered related to the study treatment or that, in the opinion of the investigator, might be life-threatening if treatment is continued.

5.12 Medical Care of Subjects After End of Study

In both treatment arms, after subjects leave the study they will continue to receive institutionally defined standard of care.

5.13 Treatment Compliance

The prescribed dosage, timing and mode of administration may not be changed. Any departures from the intended regimen must be recorded in the eCRFs.

Subjects in the BEGEDINA arm will receive their assigned study treatment via IV infusion under the supervision of a healthcare professional. Their compliance will be documented by drug accountability as described in Section 5.3.2.

Subjects in the conventional arm will be administered their assigned treatment by a healthcare professional. Details of this drug therapy will be recorded in the eCRF.

Noncompliance is defined as taking less than 80% of study medication during any evaluation period (visit to visit).

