4.4.4.1 Reason for Withdrawal/Discontinuation

All subjects are free to withdraw from participation in the study at any time, for any reason, specified or unspecified, and without prejudice to further treatment. The criteria for enrollment are to be followed explicitly.

If a subject who does not meet enrollment criteria is inadvertently enrolled, the Sponsor or Sponsor designee (Contract Research Organization [CRO]) must be contacted to evaluate if the subject is to continue treatment. In these rare cases, the investigator must obtain documented approval to allow the subject to continue study treatment.

In addition, subjects will be discontinued from study drug (but not withdrawn from the study and subsequent assessments) in the following circumstances:

- The investigator decides that the subject's treatment should be discontinued. If this decision is made because of an intolerable AE or a clinically significant laboratory value, which compromises the safety, health or welfare of the subject, the study drug is to be discontinued and appropriate measures are to be taken. The Sponsor or Sponsor designee is to be notified immediately.
- Lack of compliance with protocol.

If a subject discontinues from study drug but continues in the study for follow up, a last PK sample should be collected on the next scheduled visit after study drug discontinuation. No further samples will be required. HAMA and other scheduled assessments are to be followed as per protocol.

Subjects will be discontinued from study drug and withdrawn from the study protocol in the following circumstances:

- The subject is unwilling to continue in the study and consent is withdrawn by the subject or their legal guardian. A subject may choose to discontinue treatment but agree to be followed for study endpoints and safety, as per 4.4.4.2 below.
- Lost to follow-up.
- Death.

Subjects who are withdrawn from the study early will have early termination procedures performed as shown in the Schedule of Events (Table 19). Subjects who are withdrawn from the study will not be replaced (see Section 4.4.4.3).

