- Not related: The event or laboratory test abnormality is most likely produced by other factors such as the subject's clinical condition, intercurrent illness, or concomitant drugs, and does not follow a known response pattern to the study drug, or the temporal relationship of the event to study drug administration makes a causal relationship unlikely.
- Possibly related: The event or laboratory test abnormality follows a reasonable temporal sequence from the time of drug administration, and/or follows a known response pattern to the study drug, but could have been produced by other factors such as the subject's clinical condition, intercurrent illness, or concomitant drugs. Information on drug withdrawal may be lacking or unclear.
- Probably related: The event or laboratory test abnormality follows a reasonable temporal sequence from the time of drug administration, and/or follows a known response pattern to the study drug, and unlikely to be explained by other factors such as the subject's clinical condition, intercurrent illness, or concomitant drugs. There is a positive response to drug withdrawal. Rechallenge is not required.
- Certainly related: The event or laboratory test abnormality follows a reasonable temporal sequence from the time of drug administration, and/or follows a known response pattern to the study drug, and cannot be reasonably explained by other factors such as the subject's clinical condition, intercurrent illness, or concomitant drugs. There is a positive response to drug withdrawal. Rechallenge is positive.

Adverse Events with a causality of “Possibly”, “Probably” or “Certainly” related meet criteria of ADRs.

All efforts should be made to classify the AE according to the above categories.

Action Taken

Action taken with study treatment due to the event which bases on the following categories:

- None (when no action is undertaken with the investigational product due to the event)
- Drug temporarily withdrawn

- Drug permanently withdrawn

Outcome of AE

Adverse events may result in one of the following outcomes:

- Death (only if the AE term reported is considered to be the cause of Death. Please note: for consistency, if outcome is ‘Death’ also seriousness must be ‘Death’)
- Recovered/resolved
- Recovered with sequelae
- Recovering/resolving
- Not Recovered/resolved: the event does not resolve

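### Section 5.13 bars any change of dosage or timing and scores one omitted infusion as noncompliance, while 5.11 allows dose modification and delay for toxicity; the sections are not reconciled

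*Combined protocol and SAP*

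**What the plan says.** All references are to the protocol.

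- **5.13 Treatment Compliance.** "The prescribed dosage, timing and mode of administration may not be changed". The next sentence adds: "Any departures from the intended regimen must be recorded in the eCRFs". The section closes with the definition: "Noncompliance is defined as taking less than 80% of study medication during any evaluation period (visit to visit"). It does not mention 5.11 and makes no exception for safety.
- **5.11 Dose Modification for Toxicity.** "dose modification for toxicity is left to the discretion of the Principal Investigator", and "treatment should be delayed/withdrawn in case of severe (Grade 3 or above) toxicity considered related to the study treatment". It does not mention 5.13.
- **5.1.1.1 Special Guidance for Investigators.** An infusion must be stopped for respiratory compromise or sustained desaturation. The Medical Monitor is to be consulted before later doses after desaturation, and cases of worsening respiratory function are to be discussed individually.
- **4.4.4.1 Reason for Withdrawal/Discontinuation.** "subjects will be discontinued from study drug (but not withdrawn from the study and subsequent assessments) in the following circumstances". One of the two listed circumstances is "Lack of compliance with protocol". The other is the investigator's own decision, including for an intolerable adverse event.
- **6.2.1.1, Action Taken.** There are three entries: no action, "Drug temporarily withdrawn", and permanent withdrawal.
- **5.1.1 BEGEDINA Treatment Arm.** Eleven doses are planned (Days 1 to 5, 10, 14, 17, 21, 24 and 28), with a window of one day either side from Day 10 on.

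**The concern.** An investigator who modifies or withholds BEGEDINA under 5.11, or stops an infusion under 5.1.1.1, does what those sections allow or require and departs from the first sentence of 5.13. No text says which section governs. The compliance definition then labels the event noncompliance, because its measuring period is so short that one infusion is the whole of the period's drug. Section 4.4.4.1 uses similar language for a reason to stop drug, without saying whether it means the same thing.

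About 30 centres in Europe, the US and Canada could resolve this differently. That would affect how much BEGEDINA comparable subjects receive, which events are logged as deviations or noncompliance, and what the adverse event data show. A dose reduction made under 5.11 has no accurate code in the Action Taken field.

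**Working it through.** **1. The two dosing rules side by side.**

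| Action | 5.13, first sentence | Other section |
|---|---|---|
| Reduce a dose for toxicity | Not permitted | Investigator's discretion (5.11) |
| Delay for severe related toxicity | Not permitted as a change of timing | Directed, as delay or withdrawal (5.11) |
| Stop an infusion for respiratory compromise or desaturation | No exception stated | Required (5.1.1.1) |

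Neither 5.11 nor 5.13 cites the other, and no order of precedence is given.

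**2. Planned infusions.** Five daily doses plus six later doses: 5 + 6 = 11. This matches the total in 5.1.1.

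**3. Infusions per visit-to-visit period.** Using the dosing visits of Table 19 (Days 1, 2, 3, 4, 5, 10, 14, 17, 21, 24, 28, with Day 56 next), every period contains exactly one planned infusion. If the Day 6 to 9 columns are also counted as visits, four periods contain no planned infusion, and every period with a dose still contains one.

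**4. The 80% rule by period.** Compliance = amount given / amount planned in the period.

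- One infusion omitted: 0/1 = 0%, below 80%, so noncompliance.
- One infusion reduced by a fraction r: compliance is 1 − r, and 1 − r < 0.80 when r > 0.20. A cut of more than 20% is noncompliance; a cut of 20% or less is not. The same applies to an infusion stopped before 80% has been delivered.

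**5. The same rule over the whole course.**

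| Infusions omitted | Share of course given | Below 80%? |
|---|---|---|
| 1 | 10/11 = 90.9% | No |
| 2 | 9/11 = 81.8% | No |
| 3 | 8/11 = 72.7% | Yes |

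The visit-to-visit wording is therefore what makes a single omission noncompliant. Over the course, the threshold is first crossed at the third omission.

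**6. Link to stopping drug.** Section 5.13 defines a percentage of drug taken; 4.4.4.1 speaks of compliance with the protocol. The terms differ and neither section cites the other. Whether the first triggers the second cannot be settled from the text.

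**7. Reach into the analysis.** Section 8.2 defines a full analysis set (as randomized, used for all efficacy analyses), a safety set (at least one dose) and a pharmacokinetic set (at least one concentration value). None uses compliance. Subjects taken off drug under this list in 4.4.4.1 stay in the study for assessments.

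**The case against.** The strongest reply is that 5.13 is a general adherence rule and 5.11 a specific toxicity rule, so a hold made under 5.11 follows the protocol. Section 5.13 itself expects departures, since it asks for them to be recorded. That is probably the intent, but recording a departure does not authorise it or remove it from the noncompliance definition, and no text supplies the exemption.

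Three further points stand and limit the finding:

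- **A forced permanent stop is not stated.** A reader might infer that one held infusion obliges the site to discontinue BEGEDINA through 4.4.4.1. The documents do not support that as a rule. The Action Taken list separates temporary from permanent withdrawal, 5.1.1.1 foresees possible further doses after a stopped infusion, and 4.4.4.1 has its own entry for adverse events.
- **The one-day window is not a contradiction.** It belongs to the prescribed schedule in 5.1.1 and Table 19, so dosing within it changes nothing prescribed. Nor is a delay the same as an omission: the 0% applies to an infusion not given in its period.
- **Reduced doses are not lost.** Departures go in the eCRF, amounts used and reasons for departure go on the accountability form (5.3.2), and exposure is summarised by visit (8.3.2). Only the Action Taken field lacks an entry.

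**Conclusion.** The point holds as an internal inconsistency with a poorly scaled compliance measure. The conflict between 5.13 and 5.11 is in the current text. One omitted BEGEDINA infusion scores 0% in its period against a threshold of 80%, with 90.9% of the course given. This assumes that the periods run between the Table 19 visits and that percentages are taken against the planned dose. It is worked for BEGEDINA only, because conventional-arm schedules vary and the documents do not give them.

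The relation to the 4.4.4.1 stop is unresolved: a possible reading, not a stated rule. No primary test, significance level or analysis set is directly affected. The consequences are for site conduct, exposure in the BEGEDINA arm, deviation classification and adverse event action data. It should be corrected, but it does not threaten the primary analyses.

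**What to change.** 1. Reconcile 4.4.4.1, 5.1.1.1, 5.11 and 5.13, with cross-references. State whether safety changes that the protocol permits or requires count as noncompliance under 5.13, and how 5.13 noncompliance relates to the compliance criterion in 4.4.4.1. Which clinical rule prevails is for the sponsor; none is proposed here.
2. Define compliance over a period in which an 80% threshold can discriminate, for example the whole 11-dose course. Settle item 1 first: if the measure can lead to stopping drug, its definition has clinical consequences.
3. Add a dose-modified option to Action Taken in 6.2.1.1 and the eCRF.

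The cost is protocol wording in a few sections and one eCRF option. Sample size and efficacy analyses are unchanged.

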6.0 EFFICACY, SAFETY, AND PHARMACOKINETIC ASSESSMENTS

During assessment visits in which subjects are administered BEGEDINA the assessments must be performed according to Table 19. GvHD assessments will be used to determine whether the subject's GvHD status has progressed from baseline according to the definition of progression of disease provided in Section 6.1.1.1.

6.1 Efficacy

6.1.1 Primary Efficacy

There are two primary endpoints.

1. The OR (CR or PR) at Study Day 28.
2. TRM (any deaths without prior diagnosis of relapse) up to Study Day 180

These endpoints are both considered primary as health authorities (EMA/FDA) have requested different primary endpoints.

6.1.1.1 Overall Response to Treatment at Study Day 28

The change in grade from baseline to Study Day 28 (-1/+2 day) will be used to determine the response of GvHD to treatment using the following classifications:

- *Complete response (CR)*: complete resolution of all signs of GvHD.
- *Partial response (PR)*: improvement of 1 overall grade (i.e., change from baseline in IBMTR to a less severe grading).
- *Stable disease (SD)*: No change in GvHD grading (i.e., no change from baseline in IBMTR grade).
- *Disease progression (PD)*: Deterioration in one overall grade in GvHD (i.e., worsening in IBMTR by at least 1 grade compared to baseline).
- Death (up to Study Day 28).

Overall response at Study Day 28 (i.e. change in GvHD grade compared to baseline) is defined as

- Complete response or PR at Study Day 28 response assessment
- and no third-line therapy has been introduced prior to the Study Day 28 response assessment

Non-response at Study Day 28 is defined as

- Stable disease or PD or missing response assessment at Study Day 28 (including death up to Study Day 28) or
- Complete response or PR at Study Day 28 response assessment and third-line therapy has been introduced prior to the Study Day 28 response assessment

Response at Study Day 28 will be adjudicated by an independent blinded hematologist; this adjudicated response will be used for the primary analysis of OR at Study Day 28.

6.1.1.1.1 Grading the Severity of Acute GvHD

At the visits presented in Table 19, the severity of the subject's GvHD will be graded using the IBMTR system (see Table 21) and the Glucksberg criteria (see Table 23).

GvHD will be graded and documented by stage of each organ, with date of onset/change in stage; gut GvHD will be documented as upper GI tract (limited to anorexia, nausea, vomiting) and/or lower GI tract. This will permit also an exploratory analysis of refined response by standard-risk or high-risk GvHD at onset, in which standard risk is defined by single organ involvement (stage 1 to 3 skin or stage 1 to 2 GI) or 2 organ involvement (stage 1 to 3 skin plus stage 1 GI or stage 1 to 3 skin plus stage 1 to 4 liver), and high-risk are those which are not standard risk ([MacMillan et al., 2015](#)).

The IBMTR

For the analysis of the primary endpoint, severity of acute GvHD will be graded using the IBMTR system. In this system, severity is determined by a clinical assessment of the degree of involvement of the skin, liver and GI tract (Table 21). Grade A GvHD is characterized as mild disease, Grade B GvHD as moderate, Grade C as severe and Grade D life-threatening ([Cahn et al., 2005](#); [Przepiorka et al., 1995](#); [Rowlings et al., 1997](#)).

Table 21 Grading of Graft-versus-Host Disease According to the IBMTR System

Grade	Category	Skin	Intestine	Liver
A	Mild	1	0	0
B	Moderate	2	0	0
		0-2	1	0-1
		0-2	0-1	1
		0-2	2	0-2
		0-2	0-2	2
C	Severe	3	1	0-1
		3	0-1	1
		3	0	0
		0-3	0-3	2-3
		3	0-2	0-3
D	Life-threatening	0-3	0-3	4
		0-3	4	0-4
		4	0-4	0-4

The maximum possible grading should be selected. The highest organ stage determines the grade.
 Reference: [Cahn et al., 2005](#); [Rowlings et al., 1997](#).

Glucksberg Criteria

An overall grade for acute GvHD is obtained by first assigning a stage for each of the 3 target organs (skin, liver gut). Staging of each organ, a clinical assessment, is summarized in Table 22.

With the Glucksberg approach to grading the severity of acute GvHD, this organ staging is then combined with a functional performance status assessment, using the Eastern

Cooperative Oncology Group performance status measure, to assign an overall grade for acute GvHD, according to Glucksberg and as presented in Table 23.

Table 22 Staging of Graft-versus-Host Disease (Glucksberg Criteria)

Stage	Skin	Liver	Gastro-enteric Tract
1	Rash <25% body surface ^a	Bilirubin 2-3 mg/dL ^b	>500 mL diarrhea/day (300 mL/m ² /day) or anorexia, nausea, vomiting
2	Rash 25-50% body surface ^a	Bilirubin 3-6 mg/dL ^b	1000 mL diarrhea/day (>600 mL/m ² /day)
3	Rash >50% body surface ^a (generalized erythroderma)	Bilirubin 6-15 mg/dL ^b	>1500 mL diarrhea/day (>1000 mL/m ² /day)
4	Generalized erythroderma with bullae and desquamation	Bilirubin >15 mg/dL ^b	Severe abdominal pain with/without ileus

^a To simplify the calculation of body surface the rule of nine could be considered.

^b Cut-off value for µmol/liter.

Source: [Glucksberg et al., 1974](#).

Table 23 Overall Grade of Graft-versus-Host Disease (Glucksberg Criteria)

Grade	Staging of GvHD Disease in Target Organ			Gut	ECOG PS
	Skin	Liver			
I	1-2	0		0	0
II	1-3	1	and/or	1	0-1
III	2-3	2-3	and/or	2-4	2-3
IV	2-4	2-4	and/or	2-4	3-4

Abbreviations: ECOG, Eastern Cooperative Oncology Group; GvHD, graft-versus-host disease; PS, performance status.

Source: [Glucksberg et al., 1974](#), [Przepiorka et al, 1995](#).

For ECOG Performance Scale, see [Appendix Section 12.4](#).

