4.4.2 Exclusion Criteria

Subjects will not be entered in the study for any of the following reasons:

1. Prior second-line systemic treatment for GvHD.
2. Received agents other than steroids for primary treatment of acute GvHD.
3. Stage 1-2 skin acute GvHD alone (with no other organ involvement).
4. Acute steroid-resistant acute GvHD beyond 28 days from first-line therapy (primary treatment).
5. Evidence of severe hepatic veno-occlusive disease or sinusoidal obstruction.

6. Evidence of encephalopathy.
7. Life expectancy <3 weeks.
8. Presence of chronic GvHD ([Dignan et al., 2012](#)).
9. Second or subsequent allogeneic transplant.
10. Received a solid organ transplant (with the exception of a corneal transplant >3 months prior to screening).
11. Relapsed disease after last transplant.
12. Human immunodeficiency virus (HIV) positive.
13. Evidence of lung disease that is likely to require more than 2 liter per minute of O₂ via face mask or an estimated FiO₂ of 28% via other delivery methods in order to sustain an O₂ saturation of 92% within the next 3 days.
14. Any underlying or current medical or psychiatric condition that, in the opinion of the investigator, would interfere with the evaluation of the subject including uncontrolled infection, heart failure, pulmonary hypertension. Any other serious medical condition, as judged by the investigator, which places the subject at an unacceptable risk if he or she were to participate in the study or confounds the ability to interpret data from the study.
15. Administration of any other investigational agents (not approved by the FDA or EMA for any indication) within 30 days of randomization. Participated in any interventional clinical trial for an immunomodulatory drug, within the past 30 days or within 5 half-lives of the study treatment, whichever is the greater. Participated in any interventional clinical trial for an acute GvHD therapeutic agent or for an immunomodulatory drug, within the past 30 days or within 5 half-lives of the study treatment, whichever is the greater. Participated or is currently participating in any bone marrow derived autologous and allogeneic stem cell or gene therapy study.
16. Known hypersensitivity to murine proteins.

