5.4 Method of Assigning Subjects to Treatment Group

Once the subject meets all of the inclusion criteria and none of the exclusion criteria and has provided an informed consent, the study center will request the study medication assignment using the Interactive Voice Activated Response System (IVRS).

The subject will be randomized to either the active treatment group (BEGEDINA) or the conventional treatment arm (randomization ratio 1:1). Randomization will be stratified by the baseline GvHD severity grade to either Grade B GvHD or Grade C/D GvHD.

The randomization will be managed centrally.

Subjects must start study treatment the day of randomization. Specific randomization instructions will be provided in the study procedures manual.

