8.1 Determination of Sample Size

This study will have two primary efficacy endpoints (see Section 6.1.1).

For the primary efficacy endpoint OR at Study Day 28, it is assumed that the conventional treatment would have a response rate of 50%, and further assumed that the response rate for the BEGEDINA treatment arm would be 75%. In order to have 80% power for a one-sided test at $\alpha=0.025$, 58 patients per treatment group would be required.

For the other primary endpoint, TRM up to Study Day 180, the cumulative incidence for the conventional treatment is assumed to be 50% and the one for BEGEDINA is assumed to be 30% (relative reduction by 40%). 80% power for a one-sided log-rank test with significance level 0.025 requires a total of 103 deaths without prior diagnosis of relapse. These can be expected with 92 subjects per treatment group, provided there are no early dropouts and no diagnoses of relapse. If drop-outs or diagnoses of relapse are observed during the recruitment period, the sample size may be slightly increased, e.g., to 100 subjects per treatment group. Since the required sample size for TRM is larger than the one for overall response, a total sample size of 184 (up to 200, respectively) will be used.

Overall survival up to 180 days is the key secondary endpoint and the planned sample size provides adequate power to reject the null hypothesis of equal OS, assuming 20 to 25 percent differences in survival probabilities in favor of BEGEDINA.

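### Table 21 lists nine liver-stage-2 patterns under both Grade B and Grade C, and its two footnote rules can be read to opposite grades, so the line between partial response and stable disease at Day 28 is not fixed for them

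*Combined protocol and SAP*

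**What the plan says.** - **Grading system.** Section 6.1.1.1.1: "For the analysis of the primary endpoint, severity of acute GvHD will be graded using the IBMTR system". Table 21 maps stages of skin, intestine and liver to Grades A to D.
- **Overlapping rows** (skin / intestine / liver). One Grade B row is 0-2 / 0-2 / 2. One Grade C row is 0-3 / 0-3 / 2-3.
- **Footnote to Table 21.** "The maximum possible grading should be selected. The highest organ stage determines the grade".
- **Response.** Section 6.1.1.1 defines partial response (PR) as "improvement of 1 overall grade (i.e., change from baseline in IBMTR to a less severe grading"). Stable disease (SD) is an unchanged IBMTR grade and counts as non-response.
- **Adjudication.** Section 6.1.1.1: "Response at Study Day 28 will be adjudicated by an independent blinded hematologist". The adjudicated response is used for the primary analysis.
- **Strata.** Section 5.4: "Randomization will be stratified by the baseline GvHD severity grade to either Grade B GvHD or Grade C/D GvHD". Section 5.4 does not cite Table 21, but the grade letters are those of that table.
- **Use of the endpoint.** Overall response at Day 28 is the single primary endpoint for the FDA (Section 8.3.4). It also drives the interim rule of a one-sided p-value below 0.001 (Section 8.6).

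**The concern.** A responder definition built on change in grade needs each combination of organ stages to have one grade. Here nine combinations have two, and the footnote can be used to support either. Two careful readers could take the same recorded stages and reach different Day 28 classifications.

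Liver stage 2 ("Bilirubin 3-6 mg/dL" in Table 22) sits at the boundary. With skin and intestine at stages 0-2:
- A fall in liver stage from 3 to 2 is SD if the overlap is Grade C, and PR if it is Grade B.
- A fall from 2 to 1 is PR if the overlap is Grade C, and SD if it is Grade B.

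Neither reading is therefore uniformly stricter. At stake are the reproducibility of a primary endpoint from the recorded stages and, secondarily, consistent assignment to the B and C/D strata across about 30 centers.

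**Working it through.** **Plan's own figure.** Inputs from Section 8.1: response 50% against 75%, one-sided alpha 0.025, power 80%. With pooled variance and no continuity correction:

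n = [1.960 × √(2 × 0.625 × 0.375) + 0.842 × √(0.50 × 0.50 + 0.75 × 0.25)]² / 0.25² = (1.342 + 0.557)² / 0.0625 ≈ 57.7, so 58.

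This agrees with "58 patients per treatment group would be required". It does not depend on how Table 21 is read.

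**Step 1: enumerate the table.** Stages 0-4 in three organs give 5³ = 125 patterns, or 124 without 0/0/0. Checked against the 14 printed rows:

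| Grade(s) matched | Patterns |
|---|---|
| A only | 1 |
| B only | 16 |
| B and C | 9 |
| C only | 29 |
| D only | 61 |
| No row | 8 |
| Total | 124 |

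The nine are skin 0-2 (3 values) × intestine 0-2 (3 values) × liver 2. No other pair of grades overlaps. Exclusion criterion 3, "Stage 1-2 skin acute GvHD alone (with no other organ involvement"), removes none of them, because all nine involve the liver.

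**Step 2: apply each footnote sentence.**
- *Take the maximum grade.* All nine become C. Grade B row 0-2 / 0-2 / 2 then keeps 0 of its 9 patterns. Grade B row 0-2 / 2 / 0-2 keeps 6 of its 9.
- *The highest organ stage decides.* No key from stage to grade is printed. At highest stage 1 the table follows none (1 pattern A, 6 patterns B). At highest stage 2 or above, the uniquely graded patterns number 10 + 29 + 61 = 100, and all follow one key: stage 2 is B (10 of 10), stage 3 is C (29 of 29), stage 4 is D (61 of 61). On that inferred key the nine are B.

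**Step 3: effect on response.** One-stage decreases in a single organ: 4 starting stages × 25 combinations of the other two organs = 100 per organ, 300 in all. Of these, 32 start or end at one of the 8 patterns with no row, leaving 268 gradable. Each was classified twice, with the overlap as C and as B:

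| Move | Count | Overlap = C | Overlap = B |
|---|---|---|---|
| Liver 3 to 2, skin 0-2, intestine 0-2 | 9 | SD | PR |
| Intestine 3 to 2, liver 2, skin 0-2 | 3 | SD | PR |
| Skin 3 to 2, liver 2, intestine 0-2 | 3 | SD | PR |
| Liver 2 to 1, skin 0-2, intestine 0-2 | 9 | PR | SD |

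Total 15 + 9 = 24, and 24/268 = 9.0% (24/300 = 8.0%). Complete response does not depend on the reading.

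**Step 4: all improvements.** Day 28 response can reflect any change from baseline. Counting every gradable move in which no organ worsens and at least one improves by any number of stages, 183 of 2,916 (6.3%) change class.

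**The case against.** The strongest reply is that the plan does contain a rule. The nine B/C patterns are the only cross-grade overlap in the table, so resolving them is the only work that the maximum-grade sentence does. The rival reading needs a key that is inferred, not printed. The two sentences can also be read together: the worst organ governs, and liver stage 2 appears in a Grade C row. Redundant rows are not unusual here either: Grade C rows 3 / 1 / 0-1, 3 / 0-1 / 1 and 3 / 0 / 0 all lie inside 3 / 0-2 / 0-3.

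Much of this stands. It would be wrong to infer that the plan has no rule for the overlap; read as a tie-break, the first sentence settles all nine. But the redundant Grade C rows agree with the row that contains them. The emptied Grade B row assigns a different grade from the row that overrides it, which is a conflict and not a repetition. The second sentence, applied as the rest of the table applies it, also disagrees with the first.

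Two further points stand. The same Grade C block has no row in the extracted text for intestine 3 with liver 0-1 (8 patterns, skin 0-3). That may be a loss in extraction, so it is not counted as a defect, and the row 0-3 / 0-3 / 2-3 needs the same caution. Section 8.0 also refers further detail to a SAP whose text is not among the documents reviewed; that SAP, or instructions to the adjudicator, may already fix the derivation.

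**Conclusion.** The concern holds as an inconsistency in the rule behind a primary endpoint that should be corrected. Nine of 124 non-zero stage patterns carry two grades, and 24 of 268 gradable one-stage improvements (9%) change responder status with the reading. This rests on the rows as extracted being the rows as printed.

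A reader might infer more than the documents support:
- *That about 9% of patients would be misclassified.* The count weights every stage pattern equally. The documents give no distribution of baseline or Day 28 stages, so the share of patients is unknown.
- *That the comparison is biased toward one arm.* Switches run both ways (15 and 9), and the net direction is unknown. One blinded hematologist adjudicates response, so one reading may apply to both arms. What adjudication does not do is say which reading that is.
- *That the tests or the sample size are invalid.* Analyses use the strata as randomised (Sections 8.2 and 8.3.4), so inconsistent baseline grading would cost efficiency, not validity. The 58 per group is unaffected, and the TRM definition does not use this grade.

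**What to change.** 1. Check the whole Grade C block of Table 21 in the original PDF, including row 0-3 / 0-3 / 2-3 and whether intestine 3 with liver 0-1 has a row.
2. If the overlap is confirmed, reconcile the Grade B and Grade C rows and the two footnote sentences with the cited grading source, so that each pattern has exactly one grade. This review does not say which.
3. Keep organ staging as a clinical assessment. Derive the baseline and Day 28 grades from the recorded organ stages with that single algorithm, and give it to the adjudicator.
4. Use it for future stratification, and keep strata already assigned as randomised.
5. Fix it before the unblinded interim analysis, because the Day 28 result triggers the p < 0.001 rule.

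The cost is a short protocol clarification and some re-derivation of grades. Organ stages are already collected, so no new data are needed.
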